Testing Product Messages for Colombia

Hypotheses and Analytic Plan

NCT# NCT04567004

Version Date: 9/25/20

Hypotheses

Primary Outcomes

The overall purpose of this study is to identify the impact of nutrient warnings on product selection and other outcomes compared to GDA labels, Nutriscore labels, and a no-label control, in Colombia. The primary objectives of this study are to evaluate our hypotheses that, compared to GDA, Nutriscore, and control, a nutrient **warning** label will lead to:

1. Lower selection of the less healthy product in a set of two products as the product the consumer most wants to buy.
2. Better ability to correctly identify which product of a set of two has higher levels of sugar.

We will also explore whether the impact of the nutrient warning (vs. other study conditions) on these two primary outcomes differ by respondent's educational level.

Secondary Outcomes

We hypothesize that the nutrient warning label (compared to other label types) will:

1. Have higher perceived message effectiveness
2. Be the most discouraging label

We hypothesize that the nutrient warning label (compared to all other conditions) – and all conditions compared to the control – will:

1. Increase the ability to correctly identify the most unhealthy product when compared with two options
2. Increase the ability to correctly identify whether a single product contains excess sugar, saturated fat, or sodium
3. Lower intentions of purchasing a product high in the nutrient of concern in the next week if it were available.

Analytic Plan

We will use a two-sided critical alpha of 0.05 to conduct all statistical tests. We will use complete case analysis to handle any missing data. We will descriptively report unadjusted means (and standard deviations) and percentages for the primary and secondary outcomes. For PME, we will take the average of the 3 items for each product type if $\alpha > .70$. For all outcomes assessed between-subjects only, we will then assess whether the outcomes vary by study arm with regression models (linear for continuous outcomes and logistic for dichotomous outcomes). For outcomes with multiple measurements per-person, we will fit mixed effects linear regression models for continuous outcomes (including PME) and a mixed effects logistic regression model for binary outcomes (including product selection, label selection, identification of healthier products), treating the intercept as random to account for repeated measures. We will include indicator variables for warning message (between-subjects) and product type (within-subjects), as well as an interaction of warning message and product type. We will use postestimation commands to conduct pairwise comparisons of the predicted means to examine differences by all label types. We will correct for multiple comparisons. To evaluate the most discouraging label, we examine the proportion of participants that selected each warning label as the most discouraging and will conduct z-tests to explore statistical significance of these differences. To assess whether the effect of the warning label on the primary outcomes differs by education, we will test for an interaction of warning label with low versus high education level (specified as dummy variables), and use a Wald chunk test to determine the joint interaction. We will use postestimation commands to predict means by warning label and education level and conduct pairwise comparisons of the predicted means.

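### Label selection is listed for a mixed model whose arm contrasts cannot show which label is most discouraging, and the z-tests that can show it do not handle repeated, same-person choices

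*SAP*

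**What the plan says.** Under Secondary Outcomes, the SAP introduces the relevant hypothesis with "We hypothesize that the nutrient warning label (compared to other label types) will", and the item reads "Be the most discouraging label". The comparison is between labels. The no-label control is not one of the comparators.

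The Analytic Plan then touches this subject in two places.

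- **Mixed model.** Outcomes with several measurements per person get a mixed model. For binary outcomes this is "a mixed effects logistic regression model for binary outcomes (including product selection, label selection, identification of healthier products". A random intercept allows for the repetition within a person. On the model's terms: "We will include indicator variables for warning message (between-subjects) and product type (within-subjects", plus their interaction. Postestimation commands will then "conduct pairwise comparisons of the predicted means to examine differences by all label types".
- **Dedicated sentence.** Later in the same paragraph: "To evaluate the most discouraging label, we examine the proportion of participants that selected each warning label as the most discouraging", with z-tests of the differences. The type of z-test is not stated.

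The SAP does not define label selection, list the labels offered in the most-discouraging item, or say whether that item is asked once or once per product type.

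**The concern.** For most outcomes in this plan, the label a person saw is the exposure, so comparing arms is the same as comparing label types. Product selection is an example. For the most-discouraging item that equivalence breaks down: the label is now the response, and the arm is only what the person happened to see beforehand. A contrast between arms then asks whether prior exposure shifts the choice. It does not ask which label is chosen most, yet the plan describes these contrasts as comparing label types.

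Two things are at stake. An analyst who follows the list could report a null arm contrast as no difference between labels when one label leads clearly, or report an arm effect as if it ranked the labels. And if label selection really is repeated within person, as its place on the list implies, the z-test sentence does not say how several choices from one person become one share, or that shares from the same people are dependent.

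**Working it through.** The SAP gives no sample size, choice rate or power for this item, so there is no stated figure to reproduce. All shares and sample sizes below are assumptions. So is a choice set of three labels (warning, GDA, Nutriscore), except in one line of step 4.

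**Step 1. Which outcome is label selection?** The SAP's other outcomes are product choice, identification of the higher-sugar or less healthy product, identification of nutrient excess, perceived message effectiveness and purchase intention. None is a choice of a label. The most-discouraging item is the only match. This is an inference, not a definition.

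**Step 2. What do the arm contrasts estimate?** Take the binary outcome as choosing the warning, and let its share *p* be the same in all four arms (warning, GDA, Nutriscore, control). The log odds in each arm are ln[*p*/(1−*p*)], and an arm contrast is the difference between two such values.

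| Shares (warning/GDA/Nutriscore) | Log odds in every arm | Arm contrast | Warning − GDA | Warning − Nutriscore |
|---|---|---|---|---|
| 60/25/15 | ln(0.60/0.40) = 0.405 | 0 | +0.35 | +0.45 |
| 33/33/33 | ln(0.333/0.667) = −0.693 | 0 | 0 | 0 |
| 15/25/60 | ln(0.15/0.85) = −1.735 | 0 | −0.10 | −0.45 |

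The arm contrast is 0 in all three rows, although the warning goes from most to least chosen. The level of the log odds does change, but the planned comparisons are between predicted means and do not use that level.

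**Step 3. Simulation.** There were 4,000 runs per setting, with one choice per person. The arm test was a 3-df chi-square test of warning chosen across the four arms, standing in for the model's arm term. The between-label test was *z* = (*n*₁ − *n*₂)/√(*n*₁ + *n*₂), where *n*₁ and *n*₂ are the numbers choosing the warning and GDA. Both were two-sided at 0.05.

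| Assumed n per arm | Shares | Arm test rejects | Between-label test, correct direction |
|---|---|---|---|
| 100 | 60/25/15 | 4.6% | 100% |
| 100 | 15/25/60 | 4.9% | 89.6% (warning below GDA) |
| 250 | 60/25/15 | 4.7% | 100% |
| 250 | 15/25/60 | 4.7% | 99.95% |
| 500 | 60/25/15 | 4.6% | 100% |
| 500 | 15/25/60 | 5.3% | 100% |

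The arm test rejects at about its nominal rate whichever label leads.

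**Step 4. Dependence in the z-tests.** When each person picks one label, two shares from the same people are negatively correlated. Per person, the variance of their difference is *p*₁ + *p*₂ − (*p*₁ − *p*₂)². The independent-sample formula gives *p*₁(1 − *p*₁) + *p*₂(1 − *p*₂).

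- Three equal shares: (2/3)/(4/9) = 1.50. Actual two-sided error at nominal 0.05 is 2[1 − Φ(1.96/√1.50)] = 0.110.
- Four equal shares: ratio 1.333, error 0.090.
- 40/40/20: ratio 1.667, error 0.129.
- 45/45/10: ratio 1.818, error 0.146.

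This applies only if the unspecified z-test turns out to be the independent-sample version. If choices are also repeated over *m* product types and pooled, with within-person correlation ρ, the variance of a share grows by a further 1 + (*m* − 1)ρ. The SAP gives neither *m* nor ρ, so no figure can be put on that part.

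**The case against.** A reader might infer something stronger: that one endpoint has two incompatible analyses, that nothing says which decides it, and that the hypothesis is left without a valid test. The SAP does not support that reading, for these reasons.

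- The dedicated sentence names the endpoint and supplies both a summary and a test that compare labels, as the hypothesis requires. On ordinary reading the specific sentence governs over a word in a parenthetical list.
- The mixed model can stand beside it as a check of whether the choice varies with the label seen.
- Repeated choices would not make a z-test inapplicable, since the share choosing each label can be computed and tested within each product type.
- The link between label selection and the most-discouraging item is inferred, and the protocol, which is not at hand, may define the term.
- The arm contrast of 0 in the calculations follows from assuming equal shares across arms. It shows that an arm contrast is not a label contrast. It does not show that a wrong result will be reported.
- The outcome is secondary and the z-tests are described as exploratory.

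All of this stands, and it limits the point. It does not remove it. The plan does not call the mixed model supplementary, and it describes that model's contrasts as comparing label types, which for this outcome they do not. If label selection means something else, the list names an outcome that matches no hypothesis in the SAP. And the z-test sentence is silent on repeated choices and on dependence.

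**Conclusion.** The point holds in a limited form. If label selection is the most-discouraging item, the arm-by-product mixed model is misassigned to it as an answer to the stated hypothesis: with choice shares equal across arms, its arm contrasts are 0 and reject at about 5% whether the warning is chosen most or least. The z-tests on label shares do address the hypothesis and should be taken as the deciding analysis, but they need to be specified for same-participant, possibly repeated, choices. Were the independent-sample version used, the actual error at nominal 0.05 would be about 0.09 to 0.15 over the shares tried.

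The conclusion that the model's contrasts do not rank labels rests on the SAP's own between-subjects description of the message term and does not depend on the assumed numbers. The identity of label selection is an inference. The primary outcomes are unaffected. This should be corrected, but it does not undermine the plan.

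**What to change.** In the Analytic Plan:

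1. Define label selection. If it is the most-discouraging item, remove it from the mixed-model list, or state that the model is a supplementary check of whether the choice depends on the label previously seen.
2. State that this secondary hypothesis is decided by comparing the share choosing the warning with the share choosing each other label offered, using a test for dependent (same-participant) proportions.
3. If the item is asked for each product type, say whether the comparison is made by product or over all choices with clustering by participant.

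The analysis need not be called confirmatory.

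The cost is one or two sentences of SAP text, with no new data and no extra participants. Compared with independent-sample z-tests, intervals become wider: by √1.333 = 1.15 to √1.818 = 1.35 times at the shares tried, before any allowance for repeated choices. That width reflects the dependence already in the data.

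### Optional precision gain: education, already planned as a low/high moderator, could also be a prespecified covariate in the main models for the two primary outcomes

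*SAP*

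**What the plan says.** All passages are in the SAP, Analytic Plan, unless noted.

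- Repeated binary outcomes get a "mixed effects logistic regression model for binary outcomes (including product selection, label selection, identification of healthier products), treating the intercept as random". The terms are listed in full: "We will include indicator variables for warning message (between-subjects) and product type (within-subjects), as well as an interaction of warning message and product type". No baseline covariate is named.
- Outcomes measured once: "For all outcomes assessed between-subjects only, we will then assess whether the outcomes vary by study arm with regression models". Here, too, study arm is the only term.
- Label contrasts: "We will use postestimation commands to conduct pairwise comparisons of the predicted means to examine differences by all label types".
- Education appears as a moderator. Under Primary Outcomes the SAP says "We will also explore whether the impact of the nutrient warning (vs. other study conditions) on these two primary outcomes differ by" educational level, and the Analytic Plan will "test for an interaction of warning label with low versus high education level (specified as dummy variables").
- Missing data: "We will use complete case analysis to handle any missing data".

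The SAP does not say that education adjusts the main label comparisons, and it states no association between education and either primary outcome.

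**The concern.** Each participant sees one label condition, so differences between people limit the precision of every primary label contrast. Product type varies within a person and cannot explain those differences. Education can, if it predicts which product people choose or whether they identify the one higher in sugar. The plan already uses this variable for these two outcomes but leaves it out of the models that answer the main questions.

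Only precision is at stake. Under random assignment, leaving education out does not bias the label comparison. If education predicts the outcome, adjusting for it narrows the intervals for differences in predicted means. In the random-intercept logistic model it also shrinks the standard error of the label log-odds ratio, because education takes up part of the random-intercept variance. If education does not predict the outcome, adjustment changes almost nothing.

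**Working it through.** **Inputs.** From the SAP: a two-sided alpha of 0.05, the model terms and the low/high coding. The SAP states no sample size, power, outcome rate, ICC, items per person or education effect, so it has no figure to reproduce. Everything else is assumed: overall rate 60%, equal education groups, starting power 80%, one or four items per person, ICC 0.1 to 0.5, education gaps of 10, 20 and 30 points.

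**Formulas.** With m items per person:

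- B = ((p_high − p_low)/2)², the variance between education groups.
- W = mean of p(1 − p) over the two groups.
- R² = B / (B + W(1 + (m − 1)ICC)/m), the share of person-level variance explained by education.
- Interval narrowing = 1 − √(1 − R²).
- Power = Φ((1.96 + 0.8416)/√(1 − R²) − 1.96).

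**Worked case: 20-point gap, four items, ICC 0.3.** The rates are 70% and 50%.

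- B = 0.10² = 0.01.
- W = (0.21 + 0.25)/2 = 0.23.
- The item factor is (1 + 3 × 0.3)/4 = 0.475, and 0.23 × 0.475 = 0.10925.
- R² = 0.01/0.11925 = 0.0839, and √(1 − 0.0839) = 0.957, so intervals narrow by 4.3%.
- Power = Φ(2.8016/0.957 − 1.96) = 83.3%.

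**All cases, difference in predicted means:**

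| Items, ICC | Narrowing at 10 / 20 / 30 points | Power at 10 / 20 / 30 points |
|---|---|---|
| One item | 0.5 / 2.1 / 4.8% | 80.4 / 81.6 / 83.7% |
| Four, ICC 0.1 | 1.6 / 6.1 / 12.9% | 81.2 / 84.7 / 89.6% |
| Four, ICC 0.3 | 1.1 / 4.3 / 9.4% | 80.9 / 83.3 / 87.1% |
| Four, ICC 0.5 | 0.8 / 3.3 / 7.4% | 80.7 / 82.6 / 85.6% |

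With a 30/70 education split, four items and ICC 0.3, power is 80.7, 82.8 and 86.1%. With no gap it stays at 80%.

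**Simulation of the planned random-intercept logistic model.** Two arms of 300 and four items were assumed. The model had label, product type and their interaction, and was fitted by maximum likelihood with and without education. There were 400 runs per scenario (200 for SD 3.0). Ratio of adjusted to unadjusted standard error of the label log-odds ratio:

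| Random-intercept SD | No gap | about 10 points | about 20 points | about 30 points |
|---|---|---|---|---|
| 1.2 | 1.000 | 0.988 | 0.952 | 0.893 |
| 2.0 | 1.000 | 0.991 | 0.963 | 0.918 |
| 3.0 | 1.001 | 0.993 | 0.970 | 0.930 |

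The standard error thus falls by about 1%, 3 to 5% and 7 to 11% at the three gaps. Ratios for the difference in predicted means agree to within 0.001. The estimate barely moves: at 20 points the mean unadjusted and adjusted log-odds ratios are −0.402 and −0.401 (SD 1.2), −0.556 and −0.557 (SD 2.0), and −0.775 and −0.780 (SD 3.0).

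**Ordinary logistic regression, one measurement per person** (large-sample, arms at 65% and 55%). At gaps of 10, 20 and 30 points:

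- the log-odds ratio is larger by 1.1, 4.4 and 10.6%;
- its standard error is larger by 0.6, 2.3 and 5.3%;
- the standard error of the difference in predicted means is smaller by 0.5, 2.1 and 4.9%.

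In this model the gain shows on the predicted-mean scale, which the SAP already uses for its contrasts.

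**The case against.** The strongest reply is that nothing here is wrong. The SAP states a coherent model, and a further covariate is a matter of preference. That stands, and it is why the point is optional.

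Other objections, and what remains of them:

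- **The size is assumed throughout.** This is true. The largest figure, 89.6%, needs a 30-point gap, four items and ICC 0.1. The gain in power is also smaller in a better-powered study: with four items, ICC 0.3 and a 10-point gap, 90% becomes 90.6% and 95% becomes 95.4%.
- **The second primary outcome may gain least.** The SAP's examples of repeated binary outcomes do not mention sugar identification. If it is measured once, the four-item figures do not apply to it and the ordinary logistic results do.
- **The low/high cut-point is not given.** The moderation test needs one anyway, and the same one would serve here.
- **Complete-case analysis could offset the gain.** Anyone with missing education would drop out of an adjusted model. A missing category prevents this but is an exception to the stated rule.
- **The moderation analysis already uses education.** It yields label contrasts within education levels. It does not supply the label contrast averaged over education, which is the one that would gain precision.

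**Conclusion.** The point holds as an optional improvement. Education is planned for both primary outcomes as a moderator and is absent from the main model terms. Adding it would cost little and might help. The gain is conditional and probably small: about 1% off the standard error of the label contrast at a 10-point education gap, and 3 to 5% at 20 points, in the planned random-intercept logistic model under the assumed settings. For a single measurement, the standard error of the difference in predicted means falls by 0.5% and 2.1% at the same gaps. These are illustrations, not bounds.

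The conclusion that the present plan is valid rests on random assignment of labels. The gain rests on education predicting the outcomes, which the SAP does not state. The sponsor may reasonably decline.

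**What to change.** Before outcome data are seen, amend the model statement in the Analytic Plan as follows:

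1. Include the low/high education indicator, with the same cut-point as the moderation test, as a fixed covariate in the main model for each primary outcome, whether that model is mixed-effects or ordinary logistic. Name the cut-point there or by reference.
2. Make the pairwise label comparisons on predicted means averaged over the observed education distribution.
3. Keep participants with missing education through a missing category, stated as an exception to the complete-case rule and unused if none is missing.
4. Name the adjusted model as the main analysis and report the unadjusted model as a sensitivity analysis, so that it is clear which result counts.

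The cost is a short addition to the text, one extra model per primary outcome and the exception in item 3. If a primary outcome is measured once, its adjusted odds ratio will differ slightly from the unadjusted one, so the predicted means should carry that conclusion.

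### The z-tests for the most discouraging label have no stated variance; if each participant picks one label, the ordinary two-sample form is too liberal when shares are close

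*SAP*

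**What the plan says.** Under Secondary Outcomes the SAP writes "We hypothesize that the nutrient warning label (compared to other label types) will", among other things, "Be the most discouraging label". The label types come from the statement of purpose, which sets nutrient warnings "compared to GDA labels, Nutriscore labels, and a no-label control, in Colombia". That gives three labels (warning, GDA, Nutriscore) and an arm without a label.

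The Analytic Plan gives this hypothesis one clearly assigned test: "we examine the proportion of participants that selected each warning label as the most discouraging and will conduct z-tests". No variance form, null value or list of pairs follows. The general level is fixed by "We will use a two-sided critical alpha of 0.05 to conduct all statistical tests". Multiplicity is covered by "We will correct for multiple comparisons", which names no method and stands before the z-test sentence, so it is not certain that it reaches these tests.

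**The concern.** A question about which label is most discouraging normally lets each respondent name one. Each choice of one label is then a choice against the others, so the shares are mutually exclusive parts of a single sample. The z-test that most analysts would reach for when comparing two proportions assumes two independent samples and leaves out the negative covariance. Its standard error is then too small for shares of similar size, and labels with no true difference would be declared different more often than the plan's 0.05 allows.

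The plan deals with within-person dependence for its regression outcomes through a random intercept, but has no counterpart for this comparison. A multiplicity correction changes the threshold and leaves the faulty standard error as it is. What is at stake is whether the warning could be called more discouraging than GDA or Nutriscore on a margin that the data do not support.

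**Working it through.** **Inputs.** From the SAP: two-sided alpha 0.05 (critical value 1.96), three label types, and the warning contrasted with the other two. Assumed, because the SAP gives none of them: one pick per participant, the true shares, n, and Bonferroni as the correction. The SAP has no derived figure for this outcome to reproduce.

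**Variances.** With one pick per person, Cov(p1, p2) = −p1·p2/n, so:

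- dependent shares: Var(p1−p2) = [p1 + p2 − (p1−p2)²]/n
- two-sample, unpooled: [p1(1−p1) + p2(1−p2)]/n, which is too small by 2·p1·p2/n at every pair of shares
- two-sample, pooled, with s = p1+p2: (s − s²/2)/n

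**Per-pair type I error.** With p1 = p2 = p, both two-sample forms become 2p(1−p)/n against a true 2p/n. The ratio of assumed to true standard error is √(1−p), and the actual size is 2[1 − Φ(1.96·√(1−p))].

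| Tied share p | Actual size | True SE / assumed SE |
|---|---|---|
| 0.10 | 6.3% | 1.05 |
| 0.25 | 9.0% | 1.15 |
| 0.30 | 10.1% | 1.20 |
| 1/3 | 11.0% | 1.22 |

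For p = 1/3: √(2/3) = 0.816, 1.96 × 0.816 = 1.600, and 2[1 − Φ(1.600)] = 0.1095. If two labels tie above one third and the remaining one is rarely chosen, the rate is higher (12.9% at 0.40).

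**Two comparisons, warning against each other label.** Multinomial simulation, n = 1000, 200,000 replicates:

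| True shares | Test | Per pair | Either pair | Either, Bonferroni |
|---|---|---|---|---|
| 1/3 each | pooled two-sample | 10.9% | 19.0% | 11.8% |
| 1/3 each | dependent-share | 5.0% | 9.1% | 4.7% |
| 0.30 each, 10% choose none | pooled two-sample | 10.2% | 17.9% | 11.1% |
| 0.30 each, 10% choose none | dependent-share | 5.1% | 9.3% | 4.8% |
| 0.25 each, 25% choose none | pooled two-sample | 9.0% | 15.9% | 9.5% |
| 0.25 each, 25% choose none | dependent-share | 5.0% | 9.2% | 4.8% |

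Results at n = 500 and n = 2000 are nearly the same. The McNemar-type test behaves like the dependent-share z (5.0%, 9.1% and 4.6% at one third each).

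**Where conclusions would differ.** Take two shares that sum to s = 2/3. The smallest difference reaching p < 0.05 is 1.96·√[(s − s²/2)/n] for the pooled test and √{(1.96²·s/n)/(1 + 1.96²/n)} for the dependent-share test.

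| n | Pooled two-sample | Dependent-share |
|---|---|---|
| 500 | 5.8 points | 7.1 points |
| 1000 | 4.1 points | 5.1 points |
| 2000 | 2.9 points | 3.6 points |

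Only differences between the two limits change their result.

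**Where the pooled test stops being too liberal.** The pooled and dependent variances are equal when (p1−p2)² = s²/2, that is p1/p2 = 3 + 2√2 = 5.83. This boundary applies to the pooled form only.

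**The case against.** The strongest reply is that the SAP states no wrong formula. It says z-tests, and the dependent-share statistic is itself a z-test, so a team could follow the text as written and run a valid analysis. This stands. A reader might infer that the plan prescribes an invalid test, or that this outcome will be tested at 11%. The document supports neither. The 11% needs one pick per participant, three options, equal shares and the two-sample form, and none of these is stated. The item wording may be in a protocol or questionnaire that is not shown.

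The practical reach is also small. At assumed shares of 60/20/20 with n = 500, the pooled z is 0.40/√(0.96/1000) = 12.9 and the dependent z is 0.40/√(0.64/500) = 11.2, so the conclusion is the same. The tests are described as exploratory, the outcome is secondary, and the percentages will be reported anyway.

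Two wording points might be read as adding weight, but they do not. The phrase about each warning label does not fit a study with one warning among three label types. Since the plan uses warning terms loosely for the arm variable, it probably means each label type. Label selection also appears under the "mixed effects logistic regression model for binary outcomes (including product selection, label selection, identification of healthier products", but the SAP does not say that this is the same item, so a contradiction between two analyses cannot be claimed.

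What survives is that the choice of test belongs in the SAP. This SAP leaves open a choice whose ordinary form is wrong for one-pick data, and the multiplicity correction would not repair it.

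**Conclusion.** The point holds as a badly fixed test, not as a demonstrated error. If each participant makes one choice and the ordinary two-sample z-test is used, the per-pair type I error is about 6% to 11% for tied shares of 0.10 to one third. With three labels equally chosen, a Bonferroni correction over two comparisons still leaves about a 12% chance of a false positive. The consequence is confined to near-ties on one exploratory secondary outcome; neither primary outcome is touched. Severity is minor to moderate. Confidence is high in the arithmetic and moderate in its application, because the item's format is inferred.

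**What to change.** State in the Analytic Plan that the comparison allows for shares from the same respondents, using z = (p1−p2)/√{[p1+p2−(p1−p2)²]/n}. A 50:50 binomial (McNemar-type) test among participants choosing either label of the pair would serve equally well. Name the two comparisons, warning against GDA and warning against Nutriscore, and place them under the plan's multiplicity correction. If the item is asked more than once per person, use a person-clustered variance. As clarifications only, write label type for warning label in that sentence, and say whether label selection in the mixed-model list is this item and, if so, which analysis governs.

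The cost is a few sentences and no new data. Intervals for this outcome become about 5% wider at shares of 0.10 and about 22% wider at one third (1/√(1−p) = 1.054 and 1.225).

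### The education follow-up compares predicted means two at a time, so it gives no interval or test of how the warning's effect against each comparator differs by education

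*SAP*

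**What the plan says.** Under Hypotheses, Primary Outcomes, the SAP says the team will "explore whether the impact of the nutrient warning (vs. other study conditions) on these two primary outcomes differ" by educational level. The two outcomes are "Lower selection of the less healthy product in a set of two products" and "Better ability to correctly identify which product of a set of two has higher levels of sugar". The other conditions are GDA, Nutriscore and a no-label control.

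The Analytic Plan gives three steps for this aim:

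- "we will test for an interaction of warning label with low versus high education level (specified as dummy variables");
- "use a Wald chunk test to determine the joint interaction";
- "predict means by warning label and education level and conduct pairwise comparisons of the predicted means", by postestimation.

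Earlier in the same section it states "We will use a two-sided critical alpha of 0.05 to conduct all statistical tests" and "We will correct for multiple comparisons". It names neither the correction method nor the family of tests. It names no reference label for the dummy variables. It mentions no contrast of label effects between education levels.

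**The concern.** The question is posed for the warning against the other conditions. It therefore concerns three differences in effect: warning versus GDA, versus Nutriscore and versus control, each compared between low and high education. The joint test covers all three at once, but it does not say which one is involved and gives no size. The planned follow-up compares cell means in pairs, and a pair of cells is not a difference in effect.

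After a significant Wald test, an analyst who wants to name the comparator has only the pairs to go on. One natural reading is that a label effect significant in one education level and not in the other differs by education. That can name the wrong comparator. Comparing the same label across education levels does not help either, because such a pair also contains any overall shift of the outcome with education. At stake is the interpretation of an exploratory result.

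**Working it through.** **No figure to reproduce.** The SAP gives no sample size, rates, effect sizes or power. From the document come four arms, two education levels, two-sided alpha of 0.05 and a logistic mixed model for the binary outcomes. Everything else below is assumed.

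**Step 1: contrasts.** 4 labels × 2 education levels = 8 cells, and 8 × 7 / 2 = 28 pairs. Of these, 3 × 2 = 6 compare the warning with another label within one education level. The target for comparator X is

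(warning − X in high education) − (warning − X in low education),

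which has four non-zero weights. Each pair has two, so none of the 28 is proportional to any of the three targets. The three targets span the interaction space (rank 3). The null of the 3-df Wald test is therefore exactly that all three are zero.

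**Step 2: why pairs can mislead.** Assume 100 people per cell, one observation each.

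- Low education, 50% v 35%: difference 0.15, SE = √(0.25/100 + 0.2275/100) = 0.0691, z = 2.17, p = 0.03.
- High education, 50% v 38%: difference 0.12, SE = √(0.25/100 + 0.2356/100) = 0.0697, z = 1.72, p = 0.085.
- Difference in effect: 0.15 − 0.12 = 0.03, SE = √(0.0691² + 0.0697²) = 0.098, 95% CI −0.162 to 0.222, p = 0.76.

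One level is significant and the other is not, yet there is no evidence that the effects differ. More generally, if the true effects are equal and each level has power p, exactly one level is significant with probability 2p(1 − p): 0.32 at p = 0.8 and 0.50 at p = 0.5.

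**Step 3: simulation (all inputs assumed).** There are 400,000 draws per setting, with eight independent cell log-odds drawn as normal with variance 1/(n p(1 − p)) and n = 250 or 400 effective observations per cell. The low-education control rate is 0.50. Education changes the effect for warning versus control only, with a ratio of odds ratios of 1.82. Results are conditional on a Wald statistic above 7.815. The table shows how often GDA or Nutriscore, where nothing differs, was significant in one level only, with no education main effect. Columns 2 and 3 apply Bonferroni over the 6 within-education tests, and columns 4 and 5 over all 28 pairs.

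| Warning odds ratio v GDA, Nutriscore, control (low education) | 6 tests, n=250 | 6 tests, n=400 | 28 tests, n=250 | 28 tests, n=400 |
|---|---|---|---|---|
| 1, 1, 1 | 4.1% | 3.5% | 0.9% | 0.8% |
| 1.1, 1.1, 1.3 | 8.1% | 9.4% | 2.4% | 2.9% |
| 1.3, 1.3, 1.5 | 37% | 53% | 18% | 31% |
| 1.5, 1.35, 1.86 | 59.5% | 70.0% | 39.1% | 58.4% |
| 2, 1.8, 2.5 | 58% | 21% | 72% | 40% |
| 3, 3, 4 | 1.4% | 0.0% | 5.1% | 0.0% |

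Inverting the odds ratios, as for the first primary outcome where the warning should lower the outcome, gives the same results within 0.2 points.

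Three interaction contrasts with Holm flagged a wrong comparator in 4.4% to 6.2% of Wald-significant runs across all settings, including those with an education main effect. They flagged the right one in 56% to 69% (n=250) or 68% to 81% (n=400). With no education main effect they flagged none in 29% to 42% (n=250) or 18% to 31% (n=400).

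**Step 4: precision of one contrast.** Take the fourth row, warning versus control, n = 250. The warning rate is 1.86/2.86 = 0.650 in both levels. The control rate is 0.50 in low education and (1/1.82)/(1 + 1/1.82) = 0.355 in high. The variances are 0.0176 + 0.0176 + 0.0160 + 0.0175 = 0.0687, so SE = 0.262 and the 95% CI factor is exp(1.96 × 0.262) = 1.67. At n = 400 the SE is 0.207 and the factor 1.50. Across settings the factor is 1.64 to 1.76 at 250 and 1.48 to 1.57 at 400.

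**Step 5: scale.** A constant odds ratio of 3 takes 50% to 75% (25 points) and 75% to 90% (15 points). There is no interaction on the log-odds scale, but a 10-point difference on the probability scale.

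**The case against.** The strongest reply is that the stated question is already answered. It is exploratory, asks whether the effect differs, and gets a valid joint test whose null is exactly that none of the three effects differs by education. That stands. A reader might infer that effect modification goes untested, and the Analytic Plan shows otherwise.

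Second, the requested contrasts are coefficients of the planned model, and with any reference label at least one is printed directly. This also stands, and it is why the change is cheap. But the SAP names no reference label and does not commit to reporting or adjusting these terms. With control as reference, only warning versus control can be read off; the other two need further contrasts.

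Third, the eight predicted means allow each difference in effect to be found by subtraction. That is true of its direction and point size, but subtraction gives no uncertainty. If the means are predicted probabilities, it is also on a different scale from the Wald test.

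Fourth, the simulated harm depends on a reading rule that the SAP never states. A reader might infer that the investigators will treat significance in one education level only as a difference in effect. Nothing in the document says so, nor does it say that all 28 pairs will be compared. The percentages measure a possible misuse under assumed inputs and are not an error rate of the planned analysis.

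**Conclusion.** The point holds as a modest, nearly free improvement to an exploratory analysis. The Wald test is valid and should stay. The gap is that the only named follow-up cannot estimate, with an interval or test, how the warning's effect against a given comparator differs by education. This rests on counting cells and needs no assumption.

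The size in practice does rest on assumptions. If significance in one level only were read as a difference, the share of Wald-significant runs pointing to an unaffected comparator would run from 0% to 72%, depending on label effects, cell size and correction family. It is low when label effects are absent or very strong, and high in between. The corresponding figure for Holm-adjusted contrasts is about 4% to 6%. With no rates or cell sizes in the SAP, no single value in that range can be called the expected one.

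It would be wrong to infer that the main label comparisons are compromised. They do not use the education follow-up and are not affected.

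**What to change.** Keep the Wald test and the predicted means. In the Analytic Plan, add for each primary outcome three pre-specified interaction contrasts from the same model, high versus low education: warning versus GDA, warning versus Nutriscore and warning versus control. With warning as the reference label, these are the interaction coefficients. Report each with a 95% confidence interval on one scale named in advance; ratios of odds ratios match the Wald test. State the correction, for example Holm over the three. Say that any statement about which comparison differs by education rests on these contrasts and not on significance in one education level only. The pairwise comparisons can still be shown.

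The cost is about two sentences and six contrasts (three for each of two outcomes), with no new data or model. There are two downsides. Intervals will be wide: under the assumed rates, the ratio of odds ratios times or divided by about 1.5 to 1.8 at 250 to 400 effective observations per cell. And, with no education main effect, about 18% to 42% of significant Wald tests would come with no single comparator flagged; the report should then say that the source of the interaction was not identified.
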